6.2.4 ADVERSE AND SERIOUS ADVERSE EVENT REPORTING

All serious adverse events must be reported to the IRB according to regulatory requirements. The Principal Investigator will immediately report to the sponsor any serious adverse event, whether or not

considered study intervention related, including those listed in the protocol or package insert and must include an assessment of whether there is a reasonable possibility that the study intervention caused the event. Study endpoints that are serious adverse events (e.g., all-cause mortality) must be reported in accordance with the protocol unless there is evidence suggesting a causal relationship between the study intervention and the event (e.g., death from anaphylaxis). In that case, the investigator must immediately report the event to the sponsor.

All serious adverse events (SAEs) will be followed until satisfactory resolution or until the Principal Investigator deems the event to be chronic or the subject is stable. Other supporting documentation of the event may be requested and should be provided as soon as possible.

6.3 UNANTICIPATED PROBLEMS

6.3.1 DEFINITION OF UNANTICIPATED PROBLEMS (UP)

The Office for Human Research Protections (OHRP) considers unanticipated problems involving risks to subjects or others to include, in general, any incident, experience, or outcome that meets all of the following criteria:

- Unexpected in terms of nature, severity, or frequency given (a) the research procedures that are described in the protocol-related documents, such as the Institutional Review Board (IRB)-approved research protocol and informed consent document; and (b) the characteristics of the subject population being studied;
- Related or possibly related to participation in the research (“possibly related” means there is a reasonable possibility that the incident, experience, or outcome may have been caused by the procedures involved in the research); and
- Suggests that the research places subjects or others at a greater risk of harm (including physical, psychological, economic, or social harm) than was previously known or recognized.

6.3.2 UNANTICIPATED PROBLEM REPORTING

The investigator will report unanticipated problems (UPs) to the reviewing Institutional Review Board (IRB). The UP report will include the following information:

- Protocol identifying information: protocol title and number, PI’s name, and the IRB project number;
- A detailed description of the event, incident, experience, or outcome;
- An explanation of the basis for determining that the event, incident, experience, or outcome represents an UP;
- A description of any changes to the protocol or other corrective actions that have been taken or are proposed in response to the UP.

To satisfy the requirement for prompt reporting, UPs will be reported using the following timeline:

- UPs that are serious adverse events (SAEs) will be reported to the IRB within 10 working days of the investigator becoming aware of the event.
- Any other UP will be reported to the IRB within 10 working days of the investigator becoming aware of the problem.

7 STATISTICAL CONSIDERATIONS

7.1 STATISTICAL HYPOTHESES

- Primary Efficacy Endpoint(s):
- Change in Aerobic Capacity [Time Frame: baseline]
 - All subjects will undergo a progressive peak oxygen assessment to determine aerobic capacity at the Lakeshore Foundation Exercise Physiology Facility. Subjects will be instructed to perform arm crank ergometer (Lode) at 10W for 2 min. Every 2 min thereafter, power output will be increased by 10W until voluntary fatigue. Peak aerobic power will be defined as VO₂ at the point of failure to maintain 60-65 rotations per minute.
- Change in Aerobic Capacity [Time Frame: 16weeks post training]
 - All subjects will undergo a progressive peak oxygen assessment to determine aerobic capacity at the Lakeshore Foundation Exercise Physiology Facility. Subjects will be instructed to perform arm crank ergometer (Lode) at 10W for 2 min. Every 2 min thereafter, power output will be increased by 10W until voluntary fatigue. Peak aerobic power will be defined as VO₂ at the point of failure to maintain 60-65 rotations per minute.
- Change in Muscular Strength [Time Frame: baseline]
 - Muscle Strength Assessment. Maximal load that can be lifted in one repetition (1RM) will be assessed in both limbs for chest press, elbow flexion, and shoulder flexion maneuvers.
- Change in Muscular Strength [Time Frame: 16weeks post]
 - Muscle Strength Assessment. Maximal load that can be lifted in one repetition (1RM) will be assessed in both limbs for chest press, elbow flexion, and shoulder flexion maneuvers.
- Change in Insulin Sensitivity [Time Frame: baseline]
 - Oral glucose tolerance test. Following an overnight fast each subject will consume a 75g oral glucose load within 5 min. Blood samples will be collected immediately before and 60, 90, and 120 min following glucose ingestion for measurement of serum glucose and serum insulin.
- Change in Insulin Sensitivity [Time Frame: 16weeks post training]
 - Oral glucose tolerance test. Following an overnight fast each subject will consume a 75g oral glucose load within 5 min. Blood samples will be collected immediately before and 60, 90, and 120 min following glucose ingestion for measurement of serum glucose and serum insulin.
- Change in Blood Lipids [Time Frame: baseline]
 - Laboratory analyses. Concentrations of blood lipids will be determined in the Core Laboratory of the CCTS, NORC, and DRC.
- Change in Blood Lipids [Time Frame: 16weeks post training]
 - Laboratory analyses. Concentrations of blood lipids will be determined in the Core Laboratory of the CCTS, NORC, and DRC.
- Change in Body Composition [Time Frame: baseline]

- Dual-energy X-ray absorptiometry (DXA). Total and regional body composition will be measured by DXA (Lunar Radiation Corp., Madison, WI) at the Lakeshore Foundation Research Facility.
- Change in Body Composition [Time Frame: 16weeks post training]
 - Dual-energy X-ray absorptiometry (DXA). Total and regional body composition will be measured by DXA (Lunar Radiation Corp., Madison, WI) at the Lakeshore Foundation Research Facility.
- Change in Blood Pressure [Time Frame: baseline]
 - Systolic and Diastolic blood pressure will be assessed using standard blood pressure cuff and a stethoscope.
- Change in Blood Pressure [Time Frame: 16weeks post training]
 - Systolic and Diastolic blood pressure will be assessed using standard blood pressure cuff and a stethoscope.
- Secondary Efficacy Endpoint(s):

Semi-Structured Interview [Time Frame: 16 weeks post-training]

The semi-structured interviews will contain seven open-ended questions related to the following areas: 1) overall perceptions of the program, 2) program likes, 3) dislikes, 4) perceived satisfaction and 5) value, 6) technology and equipment usability, and 7) factors that affected adherence. These areas will be probed in greater detail by the interviewer through additional follow-up questions.

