1 PROTOCOL SUMMARY

1.1 SYNOPSIS

Title:	Telehealth high intensity interval exercise and cardiometabolic health in spinal cord injury
Study Description:	This study will determine if the implementation of a home-based telehealth high intensity interval exercise-training (HIIT) program can significantly improve cardiometabolic health and physical function in a cohort of individuals with longstanding spinal cord injury (SCI). Results from this study will determine feasibility, overall enjoyment, and health impact of implementing a home-based telehealth HIIT program in individuals with SCI.
Objectives:	The goal of this study is to integrate a home-based telehealth HIIT arm crank exercise training program in individuals with SCI and assess changes in cardiometabolic health and physical function. The secondary goal is to explore the uptake and implementation of HIIT in SCI.
Study Population:	
 1. Individuals 19-65 years old with confirmed diagnosis of traumatic SCI at the cervical or thoracic level (C7-T12), classified as A, B, C, or D (motor and sensory complete or incomplete) on the AIS scale. 2. At least 6 months post-injury.
Phase:	Not Applicable
Description of Study Intervention:	
 • HIIT training will be delivered two times per week for 16 weeks (32 sessions). Each session will be separated by at least 24-hrs. Participants will be allowed to choose the days and times that they feel exercise will fit into their schedule. The HIIT protocol will be determined based on peak anaerobic power measures during an arm crank Wingate Cycle test. HIIT will consist of 20 minutes of exercise consisting of four minutes of arm crank exercise at 5% of peak anaerobic power followed by 30 seconds at 30% of the peak anaerobic power; this cycle will be repeated four times, ending with two minutes of recovery at 5% of peak anaerobic power. • Other: No-exercise control group 
 ○ No-exercise control group
Study Duration:	3 years
Subject Duration:	6 months

INTRODUCTION

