
2 STUDY DESIGN

2.1 OVERALL DESIGN

Primary Purpose : Prevention

Allocation : Randomized

Interventional Model : Parallel Assignment

Interventional Model Description: In a longitudinal study design, 40 participants with chronic SCI will be randomly assigned to one of the two study groups (HIIT and control) in a 1:1 ratio. Randomization will be performed using the block randomization method. Randomization will be performed using the block randomization method. A randomization list will be generated and assignments will be placed into

closed envelopes and given to each study participant. Participants will be assessed at baseline and 16-wks post HIIT or control

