This platform allows the exercise trainer (telecoach) to monitor each participant's physiologic data in real-time (up to 5 second delay) while simultaneously video-conferencing and providing written instructions to the participant.. Telecoaches will utilize this system to provide immediate feedback regarding exercise intensity and movement quality during each exercise session. All exercise sessions will be performed on an upper body ergometer (UBE-BDP Table Top Upperbody Exerciser, Hudson Fitness). HIIT training will be delivered two times per week for 16 weeks (32 sessions). Each session will be separated by at least 24-hrs. Participants will be allowed to choose the days and times that they feel exercise will fit into their schedule. The HIIT protocol will be determined based on peak anaerobic power measures during an arm crank Wingate Cycle test. HIIT will consist of 20 minutes of exercise consisting of four minutes of arm crank exercise at 5% of peak anaerobic power followed by 30 seconds at 30% of the peak anaerobic power; this cycle will be repeated four times, ending with two minutes of recovery at 5% of peak anaerobic power. The use of percent workload is important as use of heart rate to prescribe exercise is not accurate in many individuals with SCI, as the sympathetic nervous system input is often impaired. Based on our preliminary data in which some participants had difficulty performing intervals using 50% of peak anaerobic power, this protocol will utilize a more modest 30% of peak anaerobic power exercise, which should be more feasible and achievable for all participants. This workload will still be higher than corresponding VO₂ peak workloads, thus will still elicit a high intensity interval session. The participants will be coached and monitored remotely via the telehealth system. Heart rate and respiratory rate will be monitored throughout each session.

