4.2 MEASURES TO MINIMIZE BIAS: RANDOMIZATION

Randomization will be performed using the block randomization method. Randomization will be performed using the block randomization method. A randomization list will be generated and assignments will be placed into closed envelopes and given to each study participant.

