7.2 SAMPLE SIZE DETERMINATION

40 participants will be randomized to home-based HIIT exercise or a no-exercise control group for 16-weeks.

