7.3 STATISTICAL ANALYSES

Descriptive statistics, such as means, standard deviations, and 95% confidence intervals, will be calculated for all study variables of interest. The primary method of analysis will be mixed models repeated measures analyses, such as repeated measures analysis of covariance. This will allow us to test the group, time, and group by time interaction effect simultaneously. An appropriate structure for the covariance matrix (e.g. the unstructured covariance matrix) will be selected for these models using the final data. The Tukey-Kramer multiple comparisons test will be used as the *post hoc* test of choice for these analyses. ***Biological variables, such as age, sex, race, and %fat, will be accounted for in these models (see Rigor and Reproducibility in Statistical Design and Power document for details)*** Overall comparisons between means of the two groups will be performed using the two-group t-test, and overall changes within groups will be examined using the paired t-test. Correlation analysis will be performed, with Pearson correlation coefficients being calculated for pairs of continuous variables. Distributions of continuous variables will be examined for normality using box plots, stem-and-leaf plots, and normal probability plots; those deviating greatly from a normal distribution will be log transformed or analyzed using appropriate nonparametric tests such as the Wilcoxon rank-sum and signed-rank tests. Multiple imputation methods may be used to address missing data for variables with moderate amounts of missing data ($\geq 10\%$) and after examining whether data are missing completely at random (MCAR), at

random (MAR), or not at random (MNAR). Statistical tests will be two-sided and will be performed using a 5% significance level. SAS software, version 9.4 or later, will be used to conduct the statistical analyses.

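### With participants necessarily unblinded, the plan describes no assessor masking or measurement safeguard for peak VO2, 1RM strength and blood pressure, half of its primary domains

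*Combined protocol and SAP*

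**What the plan says.** The synopsis (1.1) names the comparator as a "No-exercise control group". Section 2.1 has participants "randomly assigned to one of the two study groups (HIIT and control) in a 1:1 ratio", with the assignment handed to each participant in an envelope. The section headed "4.2 MEASURES TO MINIMIZE BIAS: RANDOMIZATION" describes block randomisation and the envelopes and stops there. No other section mentions masking or independence of those who measure outcomes.

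Section 7.1 lists six primary domains: aerobic capacity, muscular strength, insulin sensitivity, blood lipids, body composition and blood pressure. Three of them depend on effort or on a reading by ear:

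- **Aerobic capacity.** An arm-crank test in which "Every 2 min thereafter, power output will be increased by 10W until voluntary fatigue". The peak is taken as the VO2 when the participant can no longer hold a cadence of 60–65 rpm.
- **Muscular strength.** One-repetition maximum for three upper-body manoeuvres, with no rule on encouragement or on what counts as a valid lift.
- **Blood pressure.** "Systolic and Diastolic blood pressure will be assessed using standard blood pressure cuff and a stethoscope", with no number of readings or averaging rule.

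Each test is described in the same words for baseline and week 16. The documents do not say who performs the tests. Section 4.1.1 gives HIIT participants a remote coach: "Telecoaches will utilize this system to provide immediate feedback regarding exercise intensity". No coach is described for the control arm.

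**The concern.** Randomisation makes the arms comparable at baseline. It does not protect how outcomes are measured 16 weeks later. If a tester knows the arm, three things can differ between arms without any deliberate act: how hard the participant is urged on in the VO2 and 1RM tests, when the VO2 test is called, and how a pressure is heard and rounded. The likely direction favours HIIT.

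A difference that arises at week 16 only enters the group-by-time interaction in 7.3 exactly as a training effect would. No model, covariate or imputation can separate the two afterwards, so protection has to come from the conduct of the tests. At stake is how far a positive result on half of the primary domains can be believed.

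**Working it through.** **Inputs from the documents**
- Total sample size (7.2): "40 participants will be randomized to home-based HIIT exercise or a no-exercise control group for 16-weeks". With 1:1 allocation (2.1) this is 20 per arm.
- Test (7.3): "Statistical tests will be two-sided and will be performed using a 5% significance level".
- Section 7.2 gives no effect size, SD, power or dropout, so there is no stated power to reproduce.

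**Assumptions, none of them in the documents**
- Tester-induced shift at week 16 favouring HIIT: b = 0.1, 0.25 or 0.5 between-participant SD.
- Correlation between baseline and week 16: r = 0.5 to 0.8.
- No true effect and no dropout.

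**Step 1: unadjusted week-16 comparison.** Noncentrality λ = b × √(20/2) = 3.162 b, with 38 df and critical value 2.024. The rejection rate is the two-tailed probability beyond ±2.024 under the noncentral t.

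**Step 2: baseline-adjusted comparison.** Adjustment shrinks the residual SD by √(1 − r²), which is 0.866 at r = 0.5 and 0.600 at r = 0.8. The shift does not shrink, so λ = 3.162 b / √(1 − r²), with 37 df and critical value 2.026.

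| Shift b | λ, unadjusted | Rate | λ, r = 0.5 | Rate | λ, r = 0.8 | Rate |
|---|---|---|---|---|---|---|
| 0.1 SD | 0.316 | 6.1% | 0.365 | 6.5% | 0.527 | 8.1% |
| 0.25 SD | 0.791 | 12.0% | 0.913 | 14.4% | 1.318 | 25.0% |
| 0.5 SD | 1.581 | 33.8% | 1.826 | 42.8% | 2.635 | 72.8% |

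The nominal rate is 5%. The more precise analysis is the more sensitive to a fixed bias, because the same shift is judged against less noise.

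**Step 3: closer to the stated primary test.** With two visits, a group-by-time test compares mean changes. The SD of change is √(2(1 − r)) of the single-visit SD: 1.000 at r = 0.5 and 0.632 at r = 0.8. At r = 0.5, λ equals the unadjusted value, so the rates are again 6%, 12% and 34%. At r = 0.8, λ = 3.162 b / 0.632 = 5 b, that is 0.5, 1.25 and 2.5, and the rates are 8%, 23% and 68% (38 df). All of these lie within the span of the table.

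**Step 4: blood pressure in its own units.** Assume an SD of change of 8 to 15 mmHg. With λ = 3.162 × bias / SD and 38 df, a 3 mmHg reading bias gives a false-positive rate of 21% (SD 8) down to 9% (SD 15). A 5 mmHg bias gives 49% down to 18%.

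**The case against.** **Silence is not evidence of unblinded testing.** A reader might infer that telecoaches test the people they trained, or that testers know the arm. The documents say neither. The coaching passage concerns remote home sessions. The VO2 test takes place at a separate exercise physiology facility on a different make of ergometer. That does not establish different staff, but the telecoach as tester is conjecture. What stands is that no safeguard is described.

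**VO2 is better protected than blood pressure.** Fixed 10 W stages and a stated cadence criterion limit the tester's discretion over when the test ends. Encouragement can still change how long a participant holds the cadence, so the exposure is smaller but not nil.

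**The upper figures need strong assumptions.** The 73% requires both r = 0.8 and a pure tester artefact of 0.5 SD. That artefact is 0.5/0.6 = 0.83 residual SD, close to the 0.91 SD that 20 per arm detect with 80% power in an unadjusted t-test. Nothing in the documents supports an artefact that large. At 0.1 SD the inflation is only 1 to 3 percentage points. This objection stands in full, and the figures should be read as a range.

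**All six domains might be thought equally affected.** They are not. Lipids, OGTT glucose and insulin, and DXA are laboratory or machine measurements and less exposed to the tester. Sections 8.1.3 and 8.1.5 already provide for coded research data. The point does not extend to them.

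**Participants' own effort is a separate bias.** They know their arm and may try harder because of it. No instruction to testers removes that.

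**Conclusion.** The point holds as a gap in the written plan. Participants cannot be blinded, no assessor masking or measurement safeguard is described, and peak VO2, 1RM strength and blood pressure are open to differential encouragement or reading at week 16.

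The size cannot be taken from the documents. Under the assumptions above, the false-positive rate for one outcome runs from 6% to 34% unadjusted and from 6% to 73% with baseline adjustment, depending mainly on the assumed shift. The documents do not support concluding that testers are in fact unblinded, that coaches do the testing, or that the upper end of the range is to be expected. The case for acting is that the exposure covers half of the primary domains, cannot be corrected in the analysis, and can be reduced cheaply.

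**What to change.** In 7.1:
- Take blood pressure with an automated device at both visits, in place of cuff and stethoscope.
- Use one fixed encouragement script for the VO2 and 1RM tests, in both arms and at both visits.

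In 4.2:
- State that existing testing staff are not told the arm, and that participants are asked not to disclose it.
- State that, where existing staffing allows, a telecoach does not test participants they coached.

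The two changes to 7.1 need no additional assessor. The changes to 4.2 depend on staffing, which the documents do not describe. The costs are an automated device, a short script, some scheduling burden and occasional unmasking when a participant lets the arm slip. The intervention, sample size and visit schedule are unchanged. If such safeguards are already in use, a few sentences recording them are enough. The report should acknowledge that bias from participants' own effort remains.

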7.2 SAMPLE SIZE DETERMINATION

40 participants will be randomized to home-based HIIT exercise or a no-exercise control group for 16-weeks.

7.3 STATISTICAL ANALYSES

Descriptive statistics, such as means, standard deviations, and 95% confidence intervals, will be calculated for all study variables of interest. The primary method of analysis will be mixed models repeated measures analyses, such as repeated measures analysis of covariance. This will allow us to test the group, time, and group by time interaction effect simultaneously. An appropriate structure for the covariance matrix (e.g. the unstructured covariance matrix) will be selected for these models using the final data. The Tukey-Kramer multiple comparisons test will be used as the *post hoc* test of choice for these analyses. ***Biological variables, such as age, sex, race, and %fat, will be accounted for in these models (see Rigor and Reproducibility in Statistical Design and Power document for details)*** Overall comparisons between means of the two groups will be performed using the two-group t-test, and overall changes within groups will be examined using the paired t-test. Correlation analysis will be performed, with Pearson correlation coefficients being calculated for pairs of continuous variables. Distributions of continuous variables will be examined for normality using box plots, stem-and-leaf plots, and normal probability plots; those deviating greatly from a normal distribution will be log transformed or analyzed using appropriate nonparametric tests such as the Wilcoxon rank-sum and signed-rank tests. Multiple imputation methods may be used to address missing data for variables with moderate amounts of missing data ($\geq 10\%$) and after examining whether data are missing completely at random (MCAR), at

random (MAR), or not at random (MNAR). Statistical tests will be two-sided and will be performed using a 5% significance level. SAS software, version 9.4 or later, will be used to conduct the statistical analyses.

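### Section 7.3 names no deciding effect for its two-visit primary model and does not list the outcome's own baseline; the natural group-by-time test is valid but gives up precision at low to moderate correlation

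*Combined protocol and SAP*

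**What the plan says.** On the model, section 7.3 states: "The primary method of analysis will be mixed models repeated measures analyses, such as repeated measures analysis of covariance". It continues: "This will allow us to test the group, time, and group by time interaction effect simultaneously". None of the three effects is named as the one that decides efficacy.

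On covariates: "Biological variables, such as age, sex, race, and %fat, will be accounted for in these models". The list is open, and details are referred to a separate Rigor and Reproducibility document that is not among the supplied documents. The outcome's own baseline value is not in the list, and the visit at which %fat is taken is not stated.

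The section then adds further tests. Between the arms: "Overall comparisons between means of the two groups will be performed using the two-group t-test". It does not say whether this test uses week-16 values or changes. Within each arm: "overall changes within groups will be examined using the paired t-test".

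Section 2.1 fixes the visits: "Participants will be assessed at baseline and 16-wks post HIIT or control". Section 7.1 labels every primary endpoint as a change but lists baseline and 16 weeks as separate time frames and gives no contrast. Section 7.2 gives only the total of 40.

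**The concern.** The three effects answer different questions. Time, like the paired t-test, does not compare the arms and can be significant from a drift common to both. The group main effect averages the two visits and so halves a week-16 difference. Only group-by-time contrasts the arms on what happened after randomization, and with two complete visits it is the difference in mean change.

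In a randomized trial of 40, a change score is usually not the most precise use of a baseline that is already collected. If the deciding contrast and the role of baseline are left open, the choice can be made after the data are seen, among tests whose power differs widely.

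%fat raises a related question. Body composition is a primary endpoint ("Total and regional body composition will be measured by DXA"), and adjusting for a week-16 %fat value could remove part of the treatment effect.

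**Working it through.** **The plan's own figure.** Section 7.2 gives 40 participants, hence 20 per arm at 1:1, with no effect size, SD, power or correlation. There is no calculation to reproduce.

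**Inputs.** From the documents: 20 per arm, two visits, two-sided 5%. Assumed: SD of 1 at both visits, bivariate normal data, a week-16 effect of 0.6 SD, complete data, and a baseline to week-16 correlation r from 0.5 to 0.9.

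**Variance of the estimated difference**

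- Change score (group-by-time): 2(1 − r) × 2/20.
- ANCOVA on baseline only: (1 − r²) × 2/20 × (N − 3)/(N − 4). The last factor is 37/36 and allows for estimating one slope.
- ANCOVA on baseline plus four uninformative covariates: the factor becomes (N − 3)/(N − 8) = 37/32, for five slopes.

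Covariates entered as main effects in the two-visit mixed model cancel out of group-by-time. A fit with group, time, their interaction and four covariates gave the same estimate and standard error as the plain change-score difference (0.3728 and 0.3313 for both). The planned test therefore pays nothing for those covariates, while ANCOVA does.

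| SD of the estimate (outcome SD units) | r = 0.5 | 0.7 | 0.8 | 0.9 |
|---|---|---|---|---|
| Change score, formula | 0.316 | 0.245 | 0.200 | 0.141 |
| ANCOVA, baseline only, formula | 0.278 | 0.229 | 0.192 | 0.140 |
| ANCOVA, baseline + 4 covariates, formula | 0.294 | 0.243 | 0.204 | 0.148 |
| Change score, simulated | 0.317 | 0.245 | 0.201 | 0.142 |
| Mixed model, baseline means constrained equal, same 4 covariates, simulated | 0.281 | 0.231 | 0.195 | 0.140 |

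At r = 0.5, for example: change score √(2 × 0.5 × 0.1) = 0.316; ANCOVA √(0.75 × 0.1 × 37/36) = 0.278.

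**Break-even on variance.** The ratio of ANCOVA to change score is (1 + r)/2 times the small-sample factor. With baseline only, (1 + r)/2 × 37/36 = 1 gives r = 72/37 − 1 = 0.95. With four more covariates, (1 + r)/2 × 37/32 = 1 gives r = 64/37 − 1 = 0.73.

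**Power for 0.6 SD (simulation)**

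| | r = 0.5 | 0.7 | 0.8 | 0.9 |
|---|---|---|---|---|
| Change score | 46% | 67% | 83% | 99% |
| ANCOVA, baseline only | 56% | 72% | 86% | 99% |
| ANCOVA, baseline + 4 uninformative covariates | 50% | 67% | 82% | 97% |

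Change-score power by exact noncentral t is 45.6, 66.5, 83.2 and 98.5%. Under no effect, the change score and baseline-only ANCOVA rejected in 4.9 to 5.1% of trials.

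**The other listed effects.** The group main effect estimates 0.6/2 = 0.3 SD with per-person variance (1 + r)/2. Its power is 18.7% at r = 0.5, falling to 15.8% at r = 0.9. With no treatment effect but a drift in both arms of 0.3 SD of change, a paired t-test in 20 participants is significant 24.7% of the time and the time effect in 40 is significant 45.6% of the time.

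**The case against.** Four objections carry weight.

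*The intended test is clear enough.* Section 7.1 calls each endpoint a change, two arms are randomized, and 7.3 gives the primary label to the mixed model and not to the t-tests. This largely stands. A reader might infer that the plan could declare efficacy on a time effect, a paired t-test or the diluted group main effect. Nothing in the documents shows that intention, so the low power of the group main effect illustrates why the contrast should be named and is not a prediction for this trial.

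*Baseline adjustment may already be planned.* The wording allows analysis of covariance, the list is open and the cited document is not supplied. This stands too. A reader might infer that baseline is omitted; the text shows only that it is not specified here.

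*ANCOVA is not always better.* A reader might infer a gain at any r up to about 0.95, at a cost of one degree of freedom. That holds only if baseline is the sole covariate. With four uninformative covariates the advantage ends a little above r = 0.7. Prognostic covariates could help ANCOVA, but this was not simulated.

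*The identity with change scores needs complete data.* It does. With missing week-16 values, a likelihood-based mixed model also uses participants who have only a baseline value.

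What remains is that 7.3 itself does not name the contrast, and that the constrained-baseline model was more precise than the change score at every r examined, with the same four covariates included.

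**Conclusion.** The point holds as a gap in specification with a modest cost in precision. It is not an error of validity: group-by-time, the natural reading, holds its 5% level.

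The size depends on r, which the documents do not give. For 20 per arm, 0.6 SD, equal SDs and complete data, baseline adjustment without other covariates adds about 10 percentage points of power at r = 0.5, 5 to 6 at 0.7, 3 at 0.8 and essentially none at 0.9. To match it, the change score would need about 26, 23 and 22 per arm at the first three values, that is 12, 6 and 4 more participants. If ANCOVA carries four uninformative covariates, the gain is about 4 points at r = 0.5, nil near 0.7 and slightly negative at 0.8 to 0.9. The constrained-baseline model keeps most of the gain: an SD of the estimate of 0.281 against 0.317 at r = 0.5, narrowing to 0.140 against 0.142 at r = 0.9.

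**What to change.** In section 7.3:

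- For each primary outcome variable, make the deciding test the HIIT-minus-control difference at week 16 with its 95% confidence interval. Take it from the planned mixed model with baseline means constrained equal across arms and the planned covariates kept as main effects. ANCOVA on the outcome's baseline, with few or no other covariates, is the alternative.
- State that every covariate, including %fat, is its baseline value. Where %fat is itself the outcome, its baseline is already in the model and it should leave the covariate list.
- Label time effects and within-arm paired t-tests as descriptive, and unadjusted two-group t-tests as supportive.
- If the Rigor and Reproducibility document already specifies baseline adjustment, bring that text into 7.3.

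The contrast applies to one variable at a time. Several endpoints in 7.1 hold more than one; strength, for instance, "will be assessed in both limbs for chest press, elbow flexion, and shoulder flexion maneuvers". Choosing among them is a separate endpoint decision.

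Cost: wording only with the constrained model, with no new data or visits. With ANCOVA, one degree of freedom for baseline plus one per extra covariate, and a small loss of precision at high r.
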